5.4 Patient Discharge

Prior to discharge, patients are examined and evaluated for the presence of any adverse events that may have occurred between the operative procedure and discharge. Patient discharge from the hospital will be accomplished according to standard hospital/physician practice. Patients are eligible for discharge based on the following criteria:

- Patient is able to ambulate
- Surgical wound is confirmed as intact, with no signs of infection
- Patient bodily functions are active

Patient discharge from the hospital will be accomplished according to standard hospital/physician practice. Prior to discharge the patient may be fitted with a brace at the investigator's discretion. The brace will be removed at the 6-week follow up visit or earlier based on the Investigator's discretion.

The following data is collected at discharge:

- Static AP radiographs
- Static lateral radiographs
- Duration of hospital-stay and hospital discharge date
- Pain and antibiotic medication use
- Adverse events

Bone growth stimulators are not to be used during the course of this study. This study does not specify the use of prophylactic antibiotic medications. Medications may be administered at the discretion of the physician. After discharge, patients are not to receive

epidural spinal injections or nerve blocks for pain relief within six weeks of a scheduled study visit, as this will confound the collection of pain and function data.

Additionally, patients receiving post-procedure denervation procedures, at the index level, within the 24 month follow up evaluation period will be considered study failures.

Patients will be instructed to avoid smoking and use of systemic (IV, PO or transdermal patch) steroidal therapy during the first six weeks of post procedure bone healing and informed that this may affect their recovery. For the purposes of this study, use of inhalers containing steroids are not considered systemic use.

All patients will receive postoperative rehabilitation therapy as directed by the investigator with the objective of improving strength, flexibility and mechanics. This therapy will not be standardized as the program is required to be specific for each patient's need. Bending and lifting should be avoided during the first 6 week period postoperative period.

The discharge instructions contained in **Appendix 4** (or site equivalent) will be explained and provided to the patient upon hospital discharge.

[REDACTED]

[REDACTED]

[REDACTED]

5.6 Patient Follow-Up

Patient follow-up will be completed postoperatively; at hospital discharge, at 6 weeks and 3, 6, 12, and 24 months as outlined in the Assessment Schedule located in **Appendix 1**. After 24 months, patients will be evaluated annually, as required by FDA. The study assessments required at each follow-up visit are detailed below.

All questionnaires related to patient outcome will be completed at each visit independently by the patient prior to any clinical evaluations and will be administered by study personnel who are not healthcare providers directly associated with the study.

Patients who undergo removal, revision, or reoperation of, or supplemental fixation to, the investigational or control device will continue to be followed for safety and effectiveness outcome data.

5.6.1 Radiographic Assessment

The following radiographs will be taken during the follow-up visits. At the 6 week follow-up visit, only the standing neutral lateral and AP radiographs are taken. At the 3, 6, 12, 24 month time points, and annually as required by FDA, all listed radiographs are taken.

View	Position	Image Type
Lateral	Standing Neutral	Lateral
Lateral	Flexion-Extension	Flexion, Extension
AP	Standing Neutral	AP
AP	Lateral Bending	Left Lateral Bending, Right Lateral Bending

[REDACTED]

[REDACTED]

[REDACTED]

[REDACTED]

5.6.2 Function

The patient will complete the ODI and ZCQ Questionnaires for the purposes of measuring function. Both evaluations will be completed by the patient at their 6 week, 3, 6, 12 and 24 month follow-up visits, and annually as required by FDA.

5.6.3 Neurological Assessment

The neurological assessment will be completed and is performed by the physician or designee as specified on the site delegation/ signature log. Whenever possible, every effort should be made to use the same individual to perform a patient neurological assessment for the duration of the study. The specific postoperative neurological evaluation parameters are outlined in section 5.1.7 above. The evaluation will be completed at 6 weeks, 3, 6, 12 and 24 months, and annually as required by FDA. A decrease in any one of the measures compared to baseline will be considered an adverse event and should be documented on the appropriate CRF.

For the purposes of determining patient success for the primary endpoint, a successful neurological outcome is defined as: Maintenance or improvement in sensory, motor function, reflexes and muscle strength.

The results of this exam will be adjudicated by the CEC for the purposes of defining patient success.

5.6.4 Pain

Bilateral leg and back pain will be recorded by the patient and measured using the VAS Index. This evaluation will be completed by the patient at their 6 week, 3, 6, 12 and 24 month study follow-up visits, and annually as required by FDA.

5.6.5 Patient Satisfaction

Patient satisfaction with the procedure s/he received AFRS (investigational) or posterolateral fusion (control) will be assessed by the use of a brief satisfaction questionnaire. The questionnaire will be completed by the patient at 6 weeks, 3, 6, 12 and 24 months postoperatively, and annually as required by FDA.

5.6.6 Quality of Life

Quality of life indicators will be evaluated through the use of the SF-36 Quality of Life Questionnaire. This questionnaire will be administered to and completed by the patient at the 6 week, 3, 6, 12 and 24 months postoperative study visit time points, and annually as required by FDA.

5.6.7 Medication Use

Patient medication use, including pain injections, will be recorded and categorized by group. Medication evaluations will be completed at 6 weeks, 3, 6, 12 and 24 months, and annually as required by FDA.

Antibiotics and pain medications administered while the patient is in the recovery room after the spinal fusion surgery will not be recorded. Other medications, taken while in the recovery room, do not need to be recorded unless they are given for an AE. If a patient is medicated or receives other non-study therapy for an abnormal clinical laboratory evaluation (unless this is standard of care or for a pre-existing condition), it will be recorded as an AE. All pain medications and use of postoperative epidural injections and denervation procedures will be recorded. Patients receiving denervation procedures at the index level before the 24 month follow up visit will be considered study failures.

5.6.8 Return to Normal Activities/Work

Patient's ability to return to normal activities of daily living, utilization of rehabilitation and ability to return to work will be assessed by the use of a brief questionnaire. The questionnaire will be completed at 6 weeks, 3, 6, 12 and 24 months postoperatively and annually as required by FDA.

5.6.9 Adverse Events

Adverse events (AEs), including Serious Adverse Events (SAEs), will be captured intraoperatively and during all study follow-up visits. Adverse event definitions and reporting requirements are detailed in Section 6.0: Adverse Event Reporting. All reported AEs will be followed until resolution or completion of the study or postmarket study, as required by FDA.

5.6.10 Symptom Directed Physical Exam

A symptom directed physical examination will only be conducted during follow-up visits if a patient has reported signs or symptoms not previously identified during the previous study visit. Any abnormal findings will be recorded on the appropriate CRF.

5.7 Patient Discontinuation

All patients enrolled into the current study and who have undergone one of the study treatments, will be followed for 24 months postoperative and until all FDA requirements are met, potentially up to 10 years postoperative. Acceptable reasons for not evaluating a patient through the follow-up period include:

- a) Patient Lost to Follow-Up: Unable to locate patient despite documented attempts to notify the patient via telephone and by certified mail. A patient will not be considered lost to follow-up until the last scheduled follow-up visit (24 month study time point).
- b) Patient Request to Terminate: The patient requests to terminate his/her involvement in the study, therefore withdrawing his/her consent to participate in the study (the investigator must thoroughly document the reasons for termination).
- c) Patient Death: If possible, an autopsy and/or death certificate should be obtained in order to document the cause of death.

If a patient discontinues from the study (regardless of the reason), the investigator will record the reason for withdrawal on the appropriate CRFs. Every effort shall be made to have discontinued patients (as appropriate) return for an “Early Termination Visit” to collect the required safety evaluations as detailed in the protocol.

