1.3 Purpose

The purpose of this study is to evaluate the safety and effectiveness of the AFRS in patients with lateral, lateral recess and/or central canal stenosis due to facet degeneration at a single level from L3 to S1 who require a lumbar decompression and facetectomy compared to an instrumented posterolateral fusion control group. Safety of the AFRS device will be evaluated by the incidence, severity and device or procedure relatedness of all adverse events over the 24 month assessment period as compared to the control group. Effectiveness of the AFRS will be based on the improvement in symptom-related questionnaire scores, function, and neurological status.

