3.0 STUDY DESIGN AND METHODOLOGY

3.1 Study Design

The pivotal evaluation of the AFRS investigational device will incorporate a multi-center, prospective, randomized, and concurrently controlled study design. Up to 30 sites will enroll and treat a minimum of 300 patients and a maximum of 750 patients into the study. In addition, up to 60 training cases (two per clinical site) may be completed by participating investigators, at the discretion of the Sponsor and participating site clinicians.

The investigational group will consist of at least 200 patients who receive the AFRS device. The control group will consist of at least 100 patients who will receive an instrumented posterolateral fusion. This number is based upon the sample size required to provide reasonable assurance of safety and effectiveness using the concurrent control and allowing for 15 percent loss to follow-up. The patients will be allocated to treatment assignment using a 2:1 randomization scheme.

The outcome measures in this study will include the following: the SF-36 questionnaire, the ZCQ, the ODI, a neurological assessment, a symptomatic pain assessment, as measured with the VAS Index, a patient satisfaction questionnaire, and an independent radiological assessment. In addition, outcome measures will be included to support potential reimbursement with healthcare providers. Patients in both treatment groups will be followed for 24 months postoperatively.

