3.5 Study Endpoints

3.5.1 Primary Endpoint

The primary study endpoint for this study is individual patient success at 24 months. Individual patient success will be defined as follows and each component of the primary endpoint will be adjudicated by the Clinical Event Committee:

- Improvements in the ZCQ score by a minimum decrease of 0.5 versus baseline for both Symptom Severity (SS) and Physical Function (PF) scores.
- Maintenance or improvement in neurological outcome at 24 months.
- No subsequent surgical intervention at the level of treatment (including device failures requiring revision, removal, re-operation and supplemental fixation).
- No serious device-related adverse events (see paragraph below.)

[REDACTED]

[REDACTED]

[REDACTED]

[REDACTED]

[REDACTED]

[REDACTED]

[REDACTED]

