8.6 Missing Data and Sensitivity Analyses (Primary Objective)

By design, the analysis of the primary objective (at both the interim and final time points) will predict 2-year outcomes for any subjects without measured 2-year outcomes, based on transitions from interim states and the experience of those who went on from those states to provide complete 2-year data. This is true whether the missing 2-year outcomes are due to being enrolled later in the trial (as happens for many subjects at the interim analysis) or some other cause, such as loss to follow-up (which will likely apply at both the interim and final analyses). Several additional analyses are planned which will explore the sensitivity of the main conclusions to this prediction for subjects whose missing 2-year outcomes cannot be explained by simply being enrolled late (i.e., subjects who are known to be lost to follow-up or whose 2-year visit window has closed without a measured outcome). In these analyses and for such subjects, 2-year outcomes will be imputed according to the model described below.

As with the primary analysis, any such subject will be viewed as belonging to one of several states. These are the same states used in the primary analysis:

- no interim data
- success at 6 months
- recoverable non-success at 6 months
- failure at 6 months
- success at 1 year
- recoverable non-success at 1 year
- failure at 1 year

Interim failures can be imputed to be failures at 2 years, with certainty. For each of the remaining states, the probability of becoming a responder at 2 years will be modeled via a logistic formulation. Based on the number S and F of subjects who went on from that state to become 2-year successes and failures, respectively, a logistic regression of the following form will be fit:

$$\text{logit}(p) = \beta_0$$

where the parameter β_0 will be assigned a vague $N(0, 10^2)$ distribution. The posterior distribution for β_0 will then be shifted by a biasing constant γ and will be back-transformed to the probability scale as:

$$p^* = \text{logit}^{-1}(\beta_0 + \gamma)$$

The 2-year outcome for any subject belonging to this state but lost thereafter will be imputed based on this distribution of p^* . The case $\gamma = 0$ contains no bias and corresponds essentially to the primary analysis.

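### The Early Termination Visit is limited to safety evaluations: the ZCQ is not scheduled there, the neurological exam is not clearly included, and a leaver's 24-month result may be predicted from a state 8–12 months old or more

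*Combined protocol and SAP*

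**What the plan says.** **The visit.** Section 5.7 wants discontinued patients, where appropriate, to return for an Early Termination Visit "to collect the required safety evaluations as detailed in the protocol". No visible text lists those evaluations. The schedule in Appendix 1 has no column for the visit.

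**Safety and effectiveness.** Section 1.3 separates the two. On safety: "Safety of the AFRS device will be evaluated by the incidence, severity and device or procedure relatedness of all adverse events". On effectiveness: "Effectiveness of the AFRS will be based on the improvement in symptom-related questionnaire scores, function, and neurological status". Section 5.6.3 blurs the line for the neurological exam: "A decrease in any one of the measures compared to baseline will be considered an adverse event".

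**Primary endpoint.** Two of the four success components in section 3.5.1 need an assessment of the patient: "Improvements in the ZCQ score by a minimum decrease of 0.5 versus baseline" on both the SS and PF scores, and "Maintenance or improvement in neurological outcome at 24 months".

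**Missing 24-month results.** Under section 8.6 the primary analysis "will predict 2-year outcomes for any subjects without measured 2-year outcomes, based on transitions from interim states", at interim and final analyses alike, and this covers loss to follow-up. Section 8.4 bases the prediction on 6- and 12-month outcomes and excludes 3-month data. Known failures stay failures. Patients without 6-month data have a state of their own. Section 8.6 adds a sensitivity analysis that shifts the imputations by a constant gamma, as far as all failures or all successes.

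**Planned loss.** Section 3.1 sets the minimum sample size "allowing for 15 percent loss to follow-up".

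**The concern.** The plan makes an effort to see leavers once more, yet in words it does not ask them for the questionnaire that decides much of the primary endpoint. Take a patient who is a success at month 12, relapses, and attends a termination visit at month 18. The primary analysis gives this patient the prognosis of 1-year successes who stayed. If such patients are more frequent in one arm, that arm's success rate is overstated.

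A difference between arms is possible. Under section 5.2 site staff learn the assignment before surgery and the patient learns it afterwards, so dissatisfaction with the assigned treatment could influence withdrawal. The documents give no evidence that it will.

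There is also a contrast within the plan. Section 5.6 keeps collecting effectiveness data after a removal, revision, reoperation or supplemental fixation, when the primary result is already a failure. For leavers, whose result is unknown, section 5.7 names safety only.

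**Working it through.** The minimum of 300 patients cannot be reproduced, because the error rate, power and success rates are redacted. This point does not depend on it.

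**1. What the visit covers**
- ZCQ: section 1.3 places questionnaires under effectiveness and section 5.7 limits the visit to safety. The ZCQ is not scheduled there.
- Neurological exam: section 1.3 places it under effectiveness, but section 5.6.3 makes a decline an adverse event. Its inclusion is unclear.

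**2. Who is affected.** All of these must hold: the patient attends the visit, was last seen as a success or recoverable non-success at 6 or 12 months, and has no 24-month result.

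**3. Age of the state used.** The Appendix 1 windows are months 5–7, 10–14 and 22–26.
- 12-month state, leaving as the 24-month window opens: 22 − 14 = 8 to 22 − 10 = 12 months.
- 6-month state, leaving as the 12-month window closes: 14 − 7 = 7 to 14 − 5 = 9 months.
- 6-month state, 12-month visit missed, leaving at month 22: 22 − 7 = 15 to 22 − 5 = 17 months.

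**4. How many at most.** 15% of 300 is 45 patients, split 2:1 as 30 AFRS and 15 control. This is a ceiling. The documents do not say how many would leave actively and attend.

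**5. Illustrative size.** Prior means a/(a + b) from Table 8.4.2:
- Transition #2, which the example in section 8.4 identifies as 1-year success to 2-year success: 386.55/(386.55 + 29.09) = 0.93.
- Transition #1: 411.97/(411.97 + 644.36) = 0.39. I assume this is 1-year recoverable non-success; the figure that labels it is not shown.
- Transitions #3 to #5: 0.60, 0.80 and 0.70. Since 0.39 is the lowest of the five, another label for #1 would make the effect smaller.

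If a relapsed leaver has the prospects of a 1-year recoverable non-success, the over-credit is 0.93 − 0.39 = 0.54 per patient. The numbers of relapsers below are assumed, all among 200 AFRS patients:

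| Relapsed leavers | Over-credit in AFRS success rate |
|---|---|
| 3 | 3 × 0.54/200 = 0.8 points |
| 5 | 5 × 0.54/200 = 1.35 points |
| 8 | 8 × 0.54/200 = 2.2 points |

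The margin at the win analyses is 0.15, or 15 points (section 8.3). These priors serve only the sample-size looks. Win looks use flat priors, so the credited rate there is essentially the one observed in completers.

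**The case against.** **The documents may already cover the neurological exam, and relapse as an event.** A neurological decline is an adverse event under section 5.6.3, and section 6.1.1 lists worsening leg or back pain. A list of the visit's assessments could also lie in redacted text. This stands for the exam, so a reader who infers that it is omitted goes further than the text allows. It does not reach the ZCQ: the limit to safety is in the visible wording, and an adverse event report does not give SS and PF scores.

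**Most of the 15% cannot benefit.** Patients who cannot be located or have died attend nothing, and section 4.0 requires no follow-up once consent is withdrawn. This stands. The visit can help only those willing to come.

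**Gamma already brackets the effect.** This also stands. The analysis targets exactly these patients and runs to both extremes. It still shifts the prediction from the old state and cannot tell a relapsed leaver from a well one.

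**In-window visits may already count.** A reader might infer that a patient who terminates in the 12- or 24-month window loses a valid outcome. The documents do not say so. A site could complete the scheduled visit, for which Appendix 1 requires the ZCQ and neurological exam. No visible text settles the matter.

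**New data would not alter the primary model.** Correct for out-of-window visits: sections 8.4 and 8.6 have no state for a termination assessment. Collecting the data helps only if the SAP says how they are used.

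**Conclusion.** The point holds for patients who return for the visit, have no 24-month result and were last seen as a success or recoverable non-success. For them a primary component that could be measured is not scheduled, and the prediction uses a state that can be 8–12 months old or more.

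The likely size is modest: up to 1.35 points for 5 relapsed leavers and 0.8–2.2 for 3–8, against 15. This rests on assumed counts, all in one arm, on the assumed label of transition #1, and on priors that the win looks do not use. Equal shifts in both arms largely cancel. It could matter in a close result.

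Three stronger readings are tempting but unsupported:
- **Every leaver is predicted from a 6- or 12-month state.** Known failures and patients without 6-month data are handled separately.
- **The over-credit is 5 × 0.93/200 = 2.3 points.** That takes each relapser's chance of 24-month success as zero, whereas section 8.4 defines a recoverable non-success as someone who may still succeed.
- **The gap favours AFRS.** Nothing in the documents shows which arm would lose more relapsed patients.

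This is a cheap improvement worth making. It is not a flaw that invalidates the primary analysis.

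**What to change.** 1. **Section 5.7 and Appendix 1:** add an Early Termination column that asks consenting leavers for the ZCQ and neurological exam alongside the safety evaluations, with the ODI, VAS and SF-36 if feasible.
2. **Sections 8.4 and 8.6:** state that a termination visit inside the 6-, 12- or 24-month window counts as that visit in the primary analysis.
3. **Section 8.6:** for out-of-window visits keep the primary model and add one sensitivity analysis, next to the gamma analysis, in which the termination status replaces the older state. For example, a non-success at month 18 enters as a recoverable non-success at 1 year. Fix the mapping in advance. Keep this as a sensitivity analysis, because completers who relapse briefly at month 18 would still be classed by their 12-month visit.

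**Cost:** one schedule column and a few sentences, using existing forms and an existing exam at a visit already sought. It takes some minutes of patient time, and some leavers will decline. Those who cannot be located or have died are not helped, and out-of-window relapses remain in the primary result.

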6.0 ADVERSE EVENT REPORTING

6.1 Adverse Events

An Adverse Event (AE) is defined as any undesirable clinical occurrence in a patient, whether it is considered to be device-related or not. Adverse events may occur intraoperatively or postoperatively, and are reported on the Adverse Event Form (SA10). Conditions that existed or occurred prior to treatment in this study may only be considered adverse events if the patient’s condition worsens or requires additional treatment.

AEs will be classified and tabulated by the following:

1. Their relationship to the investigational device (AFRS implant) or control (posterolateral fusion) procedure, depending on the patient’s randomization into the trial;
2. Their relationship to the AFRS implant (investigational arm) or posterolateral fusion hardware (control arm) itself,
3. The severity of clinical event;
4. The action taken to treat the event; and
5. The outcome of the event.

Serious adverse events and deaths are considered adverse events, and will be listed and reported separately. Unanticipated adverse device effects will be recorded and reported in accordance with FDA regulations.

The determination of whether an adverse event is classified as a Serious Adverse Event (SAE) or Unanticipated Adverse Device Effect will be based on the definitions contained in this section, while also taking into account the clinical judgment of the investigator.

Adverse events will be coded by the Clinical Events Committee, based on the body system (e.g. gastrointestinal) and categorization of events appropriate to the condition.

